## 6 Treatment

### 6.1 Study treatment

The study treatment in this study refers to:

- **Investigational drug:** PDR001  
or
- **Chemotherapy:** as per investigator's choice (except for re-challenge with previously used drugs)

#### 6.1.1 Dosing regimen

**Table 6-1 Dose and treatment schedule**

Study treatments	Pharmaceutical form and route of administration	Dose	Frequency and/or Regimen
PDR001	Powder for solution for infusion	400mg	Every 4 weeks (Q4W)
Commonly used chemotherapy as per investigator's choice	As described in the drug label	As described in the drug label	As described in the drug label

PDR001 will be administered via i.v. infusion over 30 minutes (up to 2 hours, if clinically indicated) once every 4 weeks. Next dose may be delayed by up to 7 days to recover from previous AEs. If the next dose cannot be administered within the above mentioned 7-days delay, then the dose should be skipped. Dosing will resume at the scheduled dose and assessment schedule will be shifted accordingly.

#### 6.1.2 Treatment duration

All patients treated with either PDR001 or chemotherapy (per Investigator's choice) will begin treatment on Cycle 1 Day 1. Each cycle will have 28 days if treated with PDR001. Patients may be discontinued from study treatment earlier due to unacceptable toxicities, confirmed disease progression (per irRC only for patients treated with PDR001) and/or treatment is discontinued at the discretion of the investigator or the patient. Patients who discontinue study treatment should not be considered discontinued from the study (please refer to [Section 7.1.3](#) and [Section 4.3](#) for further details).

#### 6.1.3 Ancillary treatments (patients in PDR001 arm)

All patients randomized into the PDR001 arm, should not receive pre-medication to prevent infusion reaction before the first infusion of PDR001, in order to determine if pre-medication is necessary. If a patient experiences an infusion reaction, he/she may receive pre-medication on subsequent dosing days. The pre-medication should be chosen per institutional standard of care, at the discretion of the treating physician.

Acute allergic reactions should be treated as needed per institutional standard of care. In the event of anaphylactic/anaphylactoid reactions, this includes any therapy necessary to restore

normal cardiopulmonary status. If a patient experiences a Grade 3 anaphylactic/anaphylactoid reaction, the patient may only continue on the study following discussion with Novartis.

Patients should be treated in a facility equipped for cardiopulmonary resuscitation. Appropriate resuscitation equipment should be available at the bedside and a physician readily available.

Guidelines on management of PDR001 infusion reactions are provided in [Table 6-2](#).

The CTCAE category of “Infusion related reaction” should be used to describe PDR001 infusion reactions, unless the investigator considers another category, such as “Allergic reaction,” “Anaphylaxis,” or “Cytokine release syndrome” more appropriate in a specific situation.

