#### **6.2.3 Dose modifications and dose delay**

There will be no dose modifications allowed for PDR001.

All dose interruption, delay and discontinuation should be based on the worst preceding toxicity (CTCAE Version v4.03). If a patient experiences a Grade 3 PDR001-related AE, treatment with PDR001 should be interrupted unless otherwise specified in [Table 6-2](#). Refer to [Section 6.2](#) for Management of toxicities and immune related AEs. Following resolution of the toxicity to

Grade 1, patient may resume PDR001 treatment at the same dose level, if there is no evidence of disease progression.

A decision to resume treatment with PDR001 following the occurrence of a Grade 3 AE is at the discretion of the Investigator. If the investigator considers it to be in the patient's best interest to resume therapy before the toxicity has resolved to Grade 1, this may be permitted on a case by case basis, following discussion with Novartis.

If a patient experiences any Grade 4 PDR001-related AE, the treatment should be discontinued unless otherwise specified in [Table 6-2](#).

In case the infusion cannot be administered at the scheduled visit, it has to be administered as soon as possible. If the delay is between 1 and 7 days the procedures at the original schedule visit should be performed. If the delay is longer than 7 days, the procedure of the following visit should be performed.

Patients who missed 2 infusions plus 7 days should be discontinued from the study treatment and enter the Follow-up period. Exceptions may be made on a case by case basis after discussion between Novartis and the Investigator.

Patients who discontinue the study for an AE or clinically significant abnormal laboratory value must be followed as described in [Section 6.2](#).

All changes in study drug administration must be recorded on the Dose Administration Record eCRF.

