**Table 6-2 Criteria for interruption, delay, re-initiation and discontinuation of PDR001**

Worst toxicity CTCAE Grade (unless otherwise specified)	Recommended dose interruption, delay and discontinuation for PDR001 during a cycle of treatment
Infusion Reaction or Hypersensitivity reaction	
Grade 1	Decrease infusion rate until recovery of the symptoms
Grade 2	
Stop infusion immediately, and keep line open. Provide supplemental oxygen and fluids, as needed.
 
Monitor vital signs (e.g. blood pressure, pulse, respiration, and temperature) every 15 ± 5 minutes until resolution.
 
Administer medications for symptomatic relief as needed:
 
 
● Urticaria: Diphenhydramine (25 to 100 mg i.v.) as needed every 4 to 6 hours, or alternative as appropriate.
 
● Fever: Acetaminophen/paracetamol (650-1000 mg by mouth) as needed every 4 to 6 hours, or alternative as appropriate.
 
● Rigors: Meperidine 25 mg i.v. as needed every 6 hours or alternative as appropriate. Corticosteroids may be administered, as needed.
 
 
Resume infusion once infusion reaction resolves (within 8 hours of initial start of infusion):
 
Maintain dose level. Administer oral pre-medication (e.g. 1000 mg of acetaminophen/paracetamol, 50-100 mg diphenhydramine hydrochloride or alternative antihistamine), within 60 minutes of restarting the infusion.
 
Restart infusion at 50% of previous rate under continuous observation. Ensure that there is a minimum observation period of 1 hour prior to restarting the infusion.
 
If the AE recurs at the reinitiated slow rate of infusion, and despite oral pre-medication, then discontinue patient from study.

Grade 3 or Grade 4	
Discontinue infusion immediately, and discontinue patient from study.
 
Provide supplemental oxygen, fluids, and other resuscitative measures as needed. Monitor vital signs (e.g. blood pressure, pulse, respiration, and temperature) every 15 ± 5 minutes until resolution.

Neutropenia (ANC)	
Grade 3 (ANC < 1000 - 500/mm  )	Dose delay for PDR001-related Grade 3 until resolved to ≤ Grade 1
Grade 4 (ANC < 500/mm  )	Discontinue for PDR001-related Grade 4 > 7 days duration
Thrombocytopenia	

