Grade 3 (> 2.0 - 5.0 x ULN) or Grade 4 (> 5.0 x ULN)	Any Grade ≥3 PDR001-related isolated amylase or lipase abnormality that is not associated with symptoms or clinical manifestations of pancreatitis does not require dose delay or discontinuation. The Novartis Medical Monitor should be consulted for such amylase or lipase abnormalities

Worst toxicity CTCAE Grade (unless otherwise specified)	Recommended dose interruption, delay and discontinuation for PDR001 during a cycle of treatment
Cardiac general	
Grade 2 or Grade 3	Dose delay for PDR001-related $\geq$ Grade 2 until resolved $\leq$ Grade 1 Discontinue for PDR001-related Grade 3 lasting $>$ 7 days
Grade 4	Discontinue for PDR001-related Grade 4
Endocrine See Appendix 4 "Endocrinopathy Management Algorithm" for additional guidance on monitoring and management of any grade events	
Grade 2 or Grade 3	Dose delay for any Grade $\geq$ 2 PDR001-related until resolved $\leq$ Grade 1 Grade 3 PDR001-related endocrinopathies adequately controlled with only physiologic hormone replacement do not require discontinuation
Grade 4	Grade 4 PDR001-related endocrinopathies, such as adrenal insufficiency, ACTH deficiency, hyper- or hypothyroidism, or glucose intolerance, which resolve or are adequately controlled with physiologic hormone replacement (corticosteroids, thyroid hormones) or glucose-controlling agents, respectively, may not require discontinuation after discussion with and approval from the Novartis Medical Monitor.
Skin Rash/photosensitivity See Appendix 4 "Skin Adverse Event Management Algorithm" for additional guidance on monitoring and management of any grade events.	
Grade 2	In presence of Grade 2 PDR001-related skin toxicity, treatment may be resumed (even if patient experience before a Grade 3 PDR001-related toxicity)
Grade 3 or Grade 4	Dose delay for PDR001-related Grade 3 until resolved $\leq$ Grade 1 Discontinue for PDR001-related Grade 3 lasting $>$ 7 days, or PDR001-related Grade 4
Stevens-Johnson syndrome (SJS), or Lyell syndrome/toxic epidermal necrolysis (TEN)	
Any Grade	Permanently discontinue study treatment.
Gastrointestinal See Appendix 4 "GI Adverse Event Management Algorithm" for additional guidance on monitoring and management of any grade events	
Diarrhea***	
Grade 2	Dose delay for PDR001-related Grade $\geq$ 2 until resolved $\leq$ Grade 1 or baseline

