Grade 3 or Grade 4	Discontinue for any PDR001-related Grade 3 lasting $>$ 7 days, or PDR001-related Grade 4
Fatigue/Asthenia Fatigue/ Asthenia (General disorders and administration site conditions)	
Grade 3 or Grade 4	Dose delay for PDR001-related Grade 3 until resolved $\leq$ Grade 1 Discontinue for PDR001-related Grade 3 lasting $>$ 7 days, or PDR001-related Grade 4
Any Neurological toxicity See Appendix 4 "Neurological Adverse Event Management Algorithm" for additional guidance on monitoring and management of any grade events	
Grade 2	Dose delay for PDR001-related Grade $\geq$ 2 until resolved $\leq$ Grade 1

Worst toxicity CTCAE Grade (unless otherwise specified)	Recommended dose interruption, delay and discontinuation for PDR001 during a cycle of treatment
Grade 3 or 4	Discontinue for PDR001-related Grade 3 lasting > 7 days, or PDR001-related G4
Ocular (uveitis, eye pain, blurred vision)	
Grade 2	Dose delay for PDR001-related Grade $\geq$ 2 until resolved $\leq$ Grade 1 Discontinue for any Grade 2 PDR001-related uveitis, eye pain or blurred vision that does not respond to topical therapy and does not improve to Grade 1 severity within the re-treatment period OR requires systemic treatment
Grade 3 or Grade 4	Discontinue for Grade 3 PDR001-related uveitis of any duration Discontinue for PDR001-related Grade 3 lasting > 7 days, or PDR001-related Grade 4
Pulmonary (pneumonitis, bronchospasm)	
See Appendix 4 "Pulmonary Adverse Event Management Algorithm" for additional guidance on monitoring and management of any grade events.	
Grade 1	Patients with persistent Grade 1 pneumonitis after completion of a steroid taper over at least 1 month may be eligible for retreatment if discussed with and approved by Novartis Medical Monitor.
Grade 2	Dose delay for PDR001-related Grade $\geq$ 2 until resolved $\leq$ Grade 1
Grade 3 or Grade 4	Discontinuation for Grade 3 PDR001-related pneumonitis of any duration Discontinue for PDR001-related Grade 3 lasting > 7 days or PDR001-related Grade 4
Cytokine Release Syndrome (CRS)	
Grade 2 or Grade 3 or Grade 4	If CRS is suspected (very high fever and precipitous drops in blood pressure, myalgia, change in mental status) treat with corticosteroids.
Other Non-laboratory adverse events	
Grade 2	Dose delay for PDR001-related Grade $\geq$ 2 until resolved $\leq$ Grade 1

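### Protocol Section 6.1.3 leaves room to continue after a Grade 3 anaphylactic reaction, Table 6-2 says to discontinue, and no text says which prevails

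*Protocol*

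**What the plan says.** Protocol Section 6.1.3, on ancillary treatments in the PDR001 arm, states that after a Grade 3 anaphylactic or anaphylactoid reaction "the patient may only continue on the study following discussion with Novartis". It continues: "Guidelines on management of PDR001 infusion reactions are provided in" Table 6-2.

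The first block of Table 6-2 covers infusion and hypersensitivity reactions. Its shared cell for Grades 3 and 4 reads "Discontinue infusion immediately, and discontinue patient from study" and then turns to supportive care. It offers no exception and no sponsor-discussion route. The column is headed "Recommended dose interruption, delay and discontinuation for PDR001 during a cycle of treatment".

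Section 6.2.3 gives the general rule. For a Grade 3 PDR001-related event, "treatment with PDR001 should be interrupted unless otherwise specified in" Table 6-2. Later it adds: "A decision to resume treatment with PDR001 following the occurrence of a Grade 3 AE is at the discretion of the Investigator".

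The SAP does not address the matter.

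**The concern.** For one event, one text contemplates going on with PDR001 after a conversation with the sponsor and the other tells the site to stop. The decision at stake is re-exposure after a severe allergic reaction, where the protocol should give one instruction.

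Protocol Section 12 sharpens the practical question, because it forbids investigators from asking the sponsor to approve a deviation. If the table governs, a call about re-challenge could be seen as such a request. If Section 6.1.3 governs, the same call is a required step.

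**Working it through.** No calculation applies to the main point. The check is a comparison of texts.

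**1. Is it the same event?** Yes, at Grade 3. The Table 6-2 block names hypersensitivity as well as infusion reactions. Section 6.1.3 lists anaphylaxis among the alternative CTCAE categories for a PDR001 infusion reaction.

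**2. Is it the same decision?** On the natural reading, yes. Both texts use the word study, but the table's title and column heading concern PDR001, and Section 6.1.3 is about giving PDR001 infusions.

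**3. Where do the instructions diverge?**

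| Action after a Grade 3 reaction | Section 6.1.3 | Table 6-2 cell |
|---|---|---|
| Stop PDR001 | consistent | consistent |
| Continue without sponsor discussion | not allowed | not allowed |
| Continue after sponsor discussion | left open | not offered |

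Only the last row differs.

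**4. Does any text give precedence?**

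Support for reading Section 6.1.3 as the gate for departing from the table:
- The table's column heading calls its content recommended.
- The wording of Section 6.1.3 (may only) is restrictive. It fits a default of stopping, with the sponsor controlling any departure.
- Section 6.2.3 places sponsor-discussion gates in body text, outside the table. One is for resuming before recovery to Grade 1, the other for exceptions to the stop after missed infusions.

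Support for reading the table as governing:
- Section 6.1.3 itself sends infusion reactions to Table 6-2.
- Section 6.2.3 lets the table override its general Grade 3 rule on interruption.
- Some rows do carry their own sponsor route. Endocrine Grade 4 events "may not require discontinuation after discussion with and approval from the Novartis Medical Monitor", and patients with persistent Grade 1 pneumonitis "may be eligible for retreatment if discussed with and approved by Novartis Medical Monitor". The infusion and hypersensitivity block has none. This is weak evidence, given the body-text gates in Section 6.2.3.

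The sentence in Section 6.2.3 on investigator discretion does not settle it. It neither repeats the deferral to Table 6-2 nor mentions Section 6.1.3.

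**5. How many patients?** The Amendment 06 study status reports 12 patients on PDR001 at 21 May 2019. Eleven had been randomized to it, which is 11/82 = 13.4% of that arm, and one had crossed over. The documents give no rate of severe infusion reactions, so no number of affected patients can be stated.

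**The case against.** The best defence is that the texts can be read together: stop by default, and let no patient go on without the sponsor. On that view Section 6.1.3 states a necessary condition and grants nothing, and a site that discontinues breaches neither text. This softens the clash but does not remove it. A condition on continuing presupposes that continuing is possible, and the table cell does not offer it. The opposite argument, that Section 6.2.3 makes the table control, is also respectable. The two arguments lead to different outcomes, and no sentence chooses between them.

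Four further inferences are tempting and are not supported:
- *The rules conflict on every reading of study.* They do not. If the table stops PDR001 while Section 6.1.3 concerns remaining in the trial, there is no contradiction. That reading is unnatural, because Section 6.1.2 already keeps patients who stop treatment in the study without any sponsor discussion, but it exists.
- *The sponsor always writes such exceptions into the table row, so their absence here is decisive.* Section 6.2.3 shows otherwise.
- *Section 6.1.3 is defective for having no Grade 4 rule.* Table 6-2 and Section 6.2.3 cover Grade 4.
- *No first infusions remained by May 2019.* The reported last first dose, 3 August 2018, does not expressly exclude a later crossover from the control arm.

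**Conclusion.** The inconsistency is real and minor. On the natural reading, Section 6.1.3 and Table 6-2 differ on whether PDR001 can be given again after a Grade 3 anaphylactic reaction, and either text can be argued to prevail. The conclusion assumes that both passages concern PDR001 treatment and that an anaphylactic reaction to the drug falls within the table's hypersensitivity block. The wording supports both assumptions.

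A reader might infer that the table's reference to leaving the study cuts off follow-up and so biases PFS or OS. The documents do not support this. Sections 6.1.2 and 7.1.3 keep patients who stop treatment in the study, and Section 7.1.6 requires tumor assessments to continue after a stop for toxicity. The table's phrase is shorthand for stopping treatment. There is no effect on sample size, power or any efficacy analysis.

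**What to change.** Align the two texts. The default is to replace the Section 6.1.3 sentence with: *After a Grade 3 or 4 anaphylactic or anaphylactoid reaction, permanently discontinue PDR001 as in Table 6-2.* Whether to keep a Grade 3 exception is the sponsor's clinical choice. If it is kept, write it with its conditions into the Table 6-2 cell, and have Section 6.1.3 refer to that cell.

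As a wording alignment only, change the instruction to discontinue in the Grade 3/4 cell and in the recurrent Grade 2 case to *permanently discontinue study treatment*. This matches the row for Stevens-Johnson syndrome and toxic epidermal necrolysis and the distinction drawn in Sections 6.1.2 and 7.1.3.

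The cost is one sentence and two table cells in a protocol amendment. Nothing changes in the sample size, endpoints, analyses or outputs.

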#### **6.1.4 Chemotherapy treatments (patients in control arm only)**

For patients randomized into the control arm, investigators should follow local guidelines as per standard of care and approved product labels especially regarding pre-medication schemes, the contraindications, the contraceptive regimens, the dosage adjustment in case of toxicity, the patient monitoring and the prohibited or used with caution drug.

### **6.2 Safety and dose modifications (patients in PDR001 arm)**

#### **6.2.1 Anticipated risks and safety concerns of the study drug (patients in PDR001 arm)**

Appropriate eligibility criteria as well as specific dose modification and stopping rules are included in this protocol. Recommended guidelines for prophylactic or supportive treatment for expected toxicities, including management of study-drug induced AEs, i.e. infusion reaction, pneumonitis, are provided in [Table 6-2](#). Refer to preclinical toxicity data provided in the [PDR001 Investigator’s Brochure].

#### **6.2.2 Immune-related adverse events (irAEs)**

The emergence of immune related AE (irAE) may be anticipated based on general experience in clinical studies with similar class of compounds that block the negative immune regulators.

An irAE is a clinically important AE of unknown etiology associated with the study drug exposure. irAEs are typically low grade and self-limited, often occurring after multiple doses, and most frequently involving the GI tract (diarrhea/colitis), skin (rashes), liver (hepatitis), and endocrine systems (a variety of endocrinopathies). Serologic, histologic (tumor sample) and immunological assessments should be performed to verify the immune related nature of the AE, and exclude the neoplastic, infectious or metabolic origin of the AE.

#### **6.2.3 Dose modifications and dose delay**

There will be no dose modifications allowed for PDR001.

All dose interruption, delay and discontinuation should be based on the worst preceding toxicity (CTCAE Version v4.03). If a patient experiences a Grade 3 PDR001-related AE, treatment with PDR001 should be interrupted unless otherwise specified in [Table 6-2](#). Refer to [Section 6.2](#) for Management of toxicities and immune related AEs. Following resolution of the toxicity to

Grade 1, patient may resume PDR001 treatment at the same dose level, if there is no evidence of disease progression.

A decision to resume treatment with PDR001 following the occurrence of a Grade 3 AE is at the discretion of the Investigator. If the investigator considers it to be in the patient's best interest to resume therapy before the toxicity has resolved to Grade 1, this may be permitted on a case by case basis, following discussion with Novartis.

If a patient experiences any Grade 4 PDR001-related AE, the treatment should be discontinued unless otherwise specified in [Table 6-2](#).

In case the infusion cannot be administered at the scheduled visit, it has to be administered as soon as possible. If the delay is between 1 and 7 days the procedures at the original schedule visit should be performed. If the delay is longer than 7 days, the procedure of the following visit should be performed.

Patients who missed 2 infusions plus 7 days should be discontinued from the study treatment and enter the Follow-up period. Exceptions may be made on a case by case basis after discussion between Novartis and the Investigator.

Patients who discontinue the study for an AE or clinically significant abnormal laboratory value must be followed as described in [Section 6.2](#).

All changes in study drug administration must be recorded on the Dose Administration Record eCRF.

#### **6.2.4 Management of toxicities and immune related AEs (irAEs)**

All the patients whose treatment is interrupted or permanently discontinued due to an AE or clinically significant laboratory value, must be followed-up at least once a week (or more frequently if required by institutional practices, or if clinically indicated) for 4 weeks, and subsequently at approximately 4-week intervals, until resolution or stabilization of the event, whichever comes first. Appropriate clinical experts should be consulted as deemed necessary. In case of suspected irAEs, the relevant immunological assessments (e.g. rheumatoid factor, anti-DNA Ab, etc.) should be performed.

Algorithms have been provided to assist investigators in assessing and managing the following groups of irAEs: Gastrointestinal; Renal; Pulmonary; Hepatic; Endocrinopathy; Skin; and Neurological. Management Algorithms can be found in the [Appendix 4](#).

For non- immune related AE as Grade 1 or 2, treatment with PDR001 maintains dose and schedule unless it specifies in the [Table 6-2](#).

